## 6.2.1. Homeostatic Assessment (HOMA) Modeling

Insulin resistance and beta-cell function based upon fasting glucose and insulin using the homeostatic assessment (HOMA) model will be assessed. Two variables, HOMA IR (insulin resistance) and HOMA-%B (beta-cell function) will be derived. The relationship between glucose and insulin secretion, mathematically approximated using a simple nonlinear solution, is given below:

HOMA Insulin Resistance (IR) = 
$$\frac{FI}{22.5e^{-lnFG}}$$
  
HOMA Beta Function (B) =  $\frac{20 \times FI}{[FG - 3.5]}$ 

where FG = fasting glucose (mmol/L); FI = fasting insulin (mU/L); Insulin:  $1 \mu IU/mL = 6.945 \text{ pmol/L}$ . HOMA IR and HOMA-%B will not be derived if FG is <=3.5.

The descriptive statistics for HOMA-IR and HOMA-%B at baseline and at end point (DB) for the safety analysis set will include the following:

Geometric mean (GM) = exp(mean(logs));

GM mean  $\pm 1$  SD = (exp(mean(logs) - 1 SD(logs)), exp(mean(logs) + 1 SD(logs)));

where logs indicates the natural logarithm of the HOMA values.

## 6.3. Vital Signs and Physical Examination Findings

Continuous vital sign variables including weight, waist circumference, temperature, supine and standing pulse, supine and standing blood pressure (systolic and diastolic), and BMI will be summarized at each assessment time point by treatment group. BMI will be calculated as weight  $(kg)/(height (m))^2$ , at each time point that body weight is measured. The height measurement collected at screening will be used in the calculation. Changes from baseline to each postbaseline time point will be summarized. Descriptive statistics (N, mean, SD, median, minimum and maximum) will be presented.

Incidence of treatment-emergent clinically important abnormalities in vital signs during the double-blind phase, as defined in Table 5, will be summarized for subjects who had at least one postbaseline assessment for that vital sign. If the baseline value is missing, the postbaseline value will be compared against the abnormally low/abnormally high criteria. Vital sign assessments collected during follow-up will not be used for this summary.

ter Postbaseline value outside of normal limit if:		
Abnormally low	Abnormally high	
A decrease from baseline of	An increase from baseline of	
$\geq 15$ to a value $\leq 50$	$\geq 15$ to a value $\geq 100$	
A decrease from baseline of	An increase from baseline of	
$\geq 20$ to a value $\leq 90$	$\geq 20$ to a value $\geq 180$	
A decrease from baseline of	An increase from baseline of	
$\geq$ 15 to a value $\leq$ 50	$\geq 15$ to a value $\geq 105$	
A decrease from baseline of $\geq 7\%$	An increase from baseline of	
	≥7%	
<35.5°C	>37.5°C	
	Postbaseline value outside of nor Abnormally low A decrease from baseline of $\geq 15$ to a value $\leq 50$ A decrease from baseline of $\geq 20$ to a value $\leq 90$ A decrease from baseline of $\geq 15$ to a value $\leq 50$ A decrease from baseline of $\geq 7\%$ $< 35.5^{\circ}C$	

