Twelve-lead ECGs, intended for safety monitoring, will be recorded in a supine position so that the different ECG intervals (RR, PR, QRS, QT) can be measured. The ECG will be recorded until 4 regular consecutive complexes are available in good readable quality.

During the collection of ECGs, subjects should be in a quiet setting without distractions (eg, television, cell phones). Subjects should rest in a supine position for at least 5 minutes before ECG collection and should refrain from talking or moving arms or legs. If blood sampling or vital sign measurement is scheduled for the same time point as ECG recording, it is recommended that the procedures be performed in the following order: ECG, vital signs, blood draw.

Vital Signs (Pulse/Heart Rate, Blood Pressure, Temperature)

Blood pressure and pulse/heart rate measurements will be assessed in supine and standing positions with a completely automated device. Manual techniques will be used only if an automated device is not available.

Supine blood pressure and pulse/heart rate measurements should be preceded by at least 5 minutes of rest in a quiet setting without distractions (eg, television, cell phones), and standing measurements should follow. Standing measurements are to be taken after at least a full minute of standing.

In addition, oral or tympanic temperature will be measured. In the places where oral or tympanic temperature are not standard practice, axillary temperature can be used. The same temperature measure should be used throughout the study.

Physical Examination

The study investigator, or other authorized and appropriately qualified designee, will perform the physical examinations. Height will be measured at screening only. Body weight and waist circumference will be measured at screening, Day 1, and end-of-treatment/early withdrawal visit.

Body weight will be measured using a calibrated scale at each visit. Subjects will be weighed at approximately the same time of day on the same scale, wearing underwear and a gown and without shoes; they will be instructed to empty their bladders before being weighed. (Note: if disrobing for weighing is logistically impossible, the subject should be dressed as lightly as possible, with consistency from visit to visit).

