#### 6.2. Clinical Laboratory Tests

Descriptive statistics will be presented for all chemistry (including the lipid panel), hematology (including hemoglobin A1c [HbA1c]), and urinalysis (pH and specific gravity) laboratory parameters at each scheduled time point. In addition, change from baseline to all postbaseline time points will be summarized for chemistry, hematology, and urinalysis (pH and specific gravity) parameters and displayed by treatment group.

The number and percentage of subjects with treatment-emergent postbaseline markedly abnormal postbaseline values will be presented by treatment group. Clinical laboratory test values will be considered "treatment-emergent markedly abnormal" (TEMA) using the criteria defined by the sponsor listed in Attachment 3. The identification of TEMA laboratory values is based on the postbaseline value being out of range while the baseline value is either missing or within the range given in Attachment 3. If postbaseline laboratory results are above the upper limit and the baseline value is below the lower limit, then the postbaseline abnormality will also be considered TEMA. The same applies to the postbaseline value being below the lower limit with the baseline value being above the upper limit.

In addition, the number of subjects with the following shifts in chemistry laboratory values from baseline to the maximum postbaseline time point will be presented:

- Glucose:
  - from <100 mg/dL to  $\geq 126 \text{ mg/dL}$  (normal to high)
  - from <100 mg/dL to  $\geq 100 \text{ mg/dL} <126 \text{ mg/dL}$  (normal to borderline high)
  - from [ $\geq 100 \text{ mg/dL} \langle 126 \text{ mg/dL} \rangle$ ] to  $\geq 126 \text{ mg/dL}$  (borderline high to high)
- Triglycerides:
  - $\circ$  from <150 mg/dL to  $\geq$ 200 mg/dL (normal to high/very high)
  - o from <150 mg/dL to  $\geq 500 \text{ mg/dL}$  (normal to very high)
  - $\circ~$  from [ $\geq \! 150~mg/dL$   $<\!\! 200~mg/dL$ ] to  $\geq \! 200~mg/dL$  (borderline high to high/very high)
  - o from [ $\geq$ 150 mg/dL <200 mg/dL] to  $\geq$ 500 mg/dL (borderline high to very high)
  - o from [ $\geq 200 \text{ mg/dL} \langle 500 \text{ mg/dL} \rangle$ ] to  $\geq 500 \text{ mg/dL}$  (high to very high)
- Total Cholesterol

- $\circ$  from <200 mg/dL to  $\geq$ 200 mg/dL (normal to borderline high/high)
- $\circ$  from <200 mg/dL to  $\geq$ 240 mg/dL (normal to high)
- $\circ$  from <200 mg/dL to [ $\geq$ 200 mg/dL <240 mg/dL] (normal to borderline high)

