#### **Table 5: Clinically Important Abnormalities in Vital Signs**

BP = blood pressure

A listing of subjects with treatment-emergent clinically important abnormalities in vital signs will be presented.

Orthostatic hypotension is defined as an absolute decrease in systolic (>20 mm Hg) or diastolic (>10 mm Hg) blood pressure after standing for at least 1 minute relative to supine position with an increase in pulse rate of >15 beats per minute (Table 6). The number and percentage of subjects who experience treatment-emergent orthostatic hypotension outside of pre-defined limits at any time during the double-blind phase and for whom the orthostatic hypotension was not present at baseline will be tabulated. Vital sign assessments collected during follow-up will not be used for this summary.

Table 6: Abnormal Lir	nits for Orthost	tatic Hypotensior	Parameters (Changes in
Vital Signs in Standing	Relative to Sup	pine Position)	·

0 0	i /			
	Outside of normal limit if difference			
Vital Sign	(standing minus supine)			
(1) Pulse (bpm)	>15 bpm			
(2a) Systolic BP (mmHg)	<-20 mmHg			
(2b) Diastolic BP (mmHg)	< -10 mmHg			
BP = blood pressure				
Note: Orthostatic hypotension requires that conditions (1) and [(2a) or (2b)] are met.				

For subjects who are unable to stand and have the vital signs measured in a sitting or supine position instead of the standing position, the difference between standing and supine values will remain missing.

A listing of subjects with treatment-emergent orthostatic hypotension will be presented.

In addition, a by-subject listing of the physical examination data will be presented.

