#### 6.4. Electrocardiogram

Twelve-lead ECGs will be recorded in a supine position so that the different ECG intervals (RR, PR, QRS, QT) can be measured. ECGs will be assessed at screening, Baseline, and Week 6. The ECGs will be read by a central reader. The ECG variables that will be analyzed are heart rate, PR interval, RR interval, QRS interval, QT interval, and QTc using the following correction methods: Bazett's formula (QTcB) and Fridericia's formula (QTcF).

Bazett's formula:  $QTcB (msec) = QT (msec) * (HR(bpm)/60)^{0.5};$ 

Fridericia's formula:  $QTcF (msec) = QT (msec) * (HR(bpm)/60)^{0.33}$ 

Descriptive statistics for observed values and changes from average predose will be presented by treatment group for the above ECG variables at each scheduled time point. Average predose ECG is defined as the average of all ECG results collected up to and including the day of the first dose of study drug.

The identification of treatment-emergent abnormal ECG values is based on the post-baseline value (a value occurring after the first study drug administration) being out of range while the average predose value is either missing or within the limits given in **Error! Reference source not found.** If post-baseline ECG results are above the upper limits (abnormally high) and the average predose value is below the lower limits (abnormally low), then the post-baseline abnormality will also be considered treatment-emergent. The same applies to the post-baseline value being below the lower limits (abnormally low) with the average predose value being above the upper limits (abnormally high). The number and percentage of subjects with treatment-

emergent ECG values outside the pre-defined normal limits defined below will be presented for the postbaseline value by treatment group.

	Outside of normal limit if	
ECG Parameter	Abnormally low	Abnormally high
Heart Rate (bpm)	$\leq$ 50 bpm	≥100 bpm
PR interval (msec)	$\leq 120$ msec	$\geq$ 200 msec
QRS interval (msec)	$\leq 60$ msec	≥120 msec
QT interval (msec)	$\leq 200$ msec	≥500 msec

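### SAP 6.3, Table 5: temperature is the only vital sign flagged without a baseline condition, so a value out of range at baseline and again after dosing counts as treatment-emergent

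*SAP*

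**What the plan says.** SAP 6.3 announces a summary of the "Incidence of treatment-emergent clinically important abnormalities in vital signs during the double-blind phase, as defined in Table 5", for subjects with at least one postbaseline assessment of the vital sign concerned. It adds a listing of the same subjects and leaves out follow-up readings.

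Table 5 has five rows. Three need a change from baseline of at least 15, 20 or 15 units, together with crossing a limit. By their limits these are pulse, systolic pressure and diastolic pressure. One row, weight, needs a change of at least 7%. The temperature row gives only <35.5°C and >37.5°C.

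The one general baseline sentence in that paragraph concerns missing data: "If the baseline value is missing, the postbaseline value will be compared against the abnormally low/abnormally high criteria".

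Elsewhere the SAP writes out what treatment-emergent means for a measured abnormality:

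- Laboratory values (SAP 6.2): identification rests on the "postbaseline value being out of range while the baseline value is either missing or within the range given in Attachment 3"; a shift from one side of the range to the other also counts.
- ECG (SAP 6.4): the "average predose value is either missing or within the limits given in" the ECG limits table, again with opposite-direction shifts included.
- Orthostatic hypotension (also SAP 6.3): only subjects "for whom the orthostatic hypotension was not present at baseline will be tabulated".

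**The concern.** The label and the rule disagree. Treatment-emergent tells the reader that the finding was absent before dosing. For temperature the written criterion looks only at the postbaseline value, so it cannot distinguish a new abnormality from one the subject brought into the study.

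Two outputs are affected: the incidence table, where the temperature count is too high, and the by-subject listing, where individual subjects are named as having a treatment-emergent abnormality that they already had. No efficacy result, test or decision rule depends on either.

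**Working it through.** **Logic check (no assumptions needed).** Take a subject who is outside a limit at baseline and has the same value at Day 8.

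| Measure | Rule | Counted? |
|---|---|---|
| Pulse, systolic, diastolic (Table 5) | change of at least 15, 20 or 15 and limit crossed | No, change is 0 |
| Weight (Table 5) | change of at least 7% | No, change is 0% |
| Temperature (Table 5), 35.3°C then 35.3°C | postbaseline <35.5°C | **Yes** |
| Laboratory (6.2) | baseline missing, in range or opposite side | No |
| ECG (6.4) | average predose missing, in range or opposite side | No |
| Orthostatic hypotension (6.3) | not present at baseline | No |

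The missing-baseline sentence does not change the temperature line, because here the baseline is present. A usable baseline exists: SAP 2.4 defines it as the closest measurement at or before the first dose.

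**Size (illustration only).** The plan states no temperature mean, SD or rate, so there is no figure to reproduce. The three postbaseline readings (Days 8, 22 and 42) come from the protocol's Time and Events Schedule, and 280 is the planned number randomized. The means, SD and correlation below are assumed, with no drug effect.

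Let a subject's own mean s be normal with mean μ and SD 0.4√ρ, and let each reading vary about s with SD 0.4√(1−ρ). Write p(s) = Φ((35.5 − s) / (0.4√(1−ρ))). Then:

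- flagged low as written = E[1 − (1 − p)³]
- flagged low and already low at baseline = E[p × (1 − (1 − p)³)]

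| Assumed μ | Flagged low, ρ = 0.4 / 0.6 | Of these, also low at baseline | Share of flags | Subjects of 280 |
|---|---|---|---|---|
| 36.5°C | 1.7% / 1.6% | 0.11% / 0.21% | 6% / 13% | 0.3 / 0.6 |
| 36.3°C | 6.0% / 5.4% | 0.68% / 1.07% | 11% / 20% | 1.9 / 3.0 |
| 36.0°C | 24% / 21% | 5.7% / 7.0% | 24% / 33% | 16 / 20 |

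The last column is the third times 280; for example 0.0021 × 280 = 0.6. The table covers the low limit only. At μ = 36.5°C, midway between the limits, symmetry adds the same amount at the high limit, giving 0.6 to 1.2 subjects in total. At 36.0°C the high limit adds almost nothing.

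A separate simulation used both limits and other assumed between/within-subject SDs (0.2/0.3, 0.3/0.2 and 0.3/0.3°C). At mean 36.6°C, adding the baseline condition lowers the flagged share by 0.07, 0.31 and 0.71 percentage points (2.11 to 2.04, 1.82 to 1.51, 5.67 to 4.96), or 0.2, 0.9 and 2.0 of 280. At mean 36.0°C it falls by 3.63, 5.73 and 7.41 points (20.47 to 16.84, 16.13 to 10.40, 25.46 to 18.05), or 10, 16 and 21 of 280. The range is much the same.

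All counts assume that every subject has all three visits. The plan's 25% dropout assumption would lower them.

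**The case against.** **The baseline condition is implied.** The summary carries the treatment-emergent label, and the missing-baseline sentence would be redundant for temperature if baseline were meant to be ignored. A programmer might apply the usual meaning. This shows what was probably intended. It does not rescue the text, because the summary is expressly defined by Table 5 and Table 5 gives temperature a complete criterion without baseline.

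**The protocol asks only for a simple count.** Protocol 11.7 calls for the percentage of subjects beyond limits of clinical importance and sets no baseline condition. That is correct, so the conflict is with the SAP's label and not with the protocol. It also provides a second way to fix the point.

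**The consequence is small.** The table is descriptive, the rule is identical in all arms, and SAP 6.3 separately summarizes temperature and its change from baseline. This stands. The extra counts tend to dilute a comparison between arms; they do not create a drug signal.

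**Stronger readings that a reader might infer.** One is that a pre-dose reading is itself counted. It is not: Table 5 requires a postbaseline value outside the limits. Another is that sites using axillary thermometry would be worst affected, because Protocol 9.6 says "In the places where oral or tympanic temperature are not standard practice, axillary temperature can be used" while Table 5 has one pair of limits. The documents do not support that. They give no offset between methods, no number of such sites and no rates. Protocol 9.6 also says "The same temperature measure should be used throughout the study", so any method offset should affect baseline and later readings alike.

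**Conclusion.** The point holds on the text alone. Temperature is the only Table 5 row with no baseline condition, and a subject out of range in the same direction before and after dosing is counted and listed as treatment-emergent, contrary to the label and to the SAP's own practice in 6.2, 6.4 and elsewhere in 6.3.

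The size is not known from the documents. Under the main set of assumed inputs it runs from fewer than 1 to about 20 of 280 subjects at the low limit. The upper end requires the whole study population to have a mean near 36.0°C, so it should not be read as an expected value. In a descriptive safety table with the same rule in every arm, this is a minor correction worth making, not a threat to the safety conclusions.

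**What to change.** Add one sentence to SAP 6.3: a temperature below 35.5°C or above 37.5°C is treatment-emergent only if the baseline value is missing, lies within 35.5 to 37.5°C, or is out of range in the opposite direction. This is the pattern already used in 6.2 and 6.4.

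Alternatively, keep the Table 5 criterion, remove the treatment-emergent label from the temperature row and its listing, and report it simply as readings beyond the limits, in line with Protocol 11.7.

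The first option costs one SAP line and one programming condition, needs no new data and leaves the efficacy analyses untouched. Its drawback should be stated: a subject who goes from 37.6°C at baseline to 39.5°C would no longer be flagged in this table. That change would still enter the change-from-baseline summary, which reports minimum and maximum as well as the mean. The second option has no such loss but gives up the treatment-emergent count for temperature.

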#### **Table 5: Clinically Important Abnormalities in Vital Signs**

BP = blood pressure

A listing of subjects with treatment-emergent clinically important abnormalities in vital signs will be presented.

Orthostatic hypotension is defined as an absolute decrease in systolic (>20 mm Hg) or diastolic (>10 mm Hg) blood pressure after standing for at least 1 minute relative to supine position with an increase in pulse rate of >15 beats per minute (Table 6). The number and percentage of subjects who experience treatment-emergent orthostatic hypotension outside of pre-defined limits at any time during the double-blind phase and for whom the orthostatic hypotension was not present at baseline will be tabulated. Vital sign assessments collected during follow-up will not be used for this summary.

Table 6: Abnormal Lir	nits for Orthost	tatic Hypotensior	Parameters (Changes in
Vital Signs in Standing	Relative to Sup	pine Position)	·

0 0	i /			
	Outside of normal limit if difference			
Vital Sign	(standing minus supine)			
(1) Pulse (bpm)	>15 bpm			
(2a) Systolic BP (mmHg)	<-20 mmHg			
(2b) Diastolic BP (mmHg)	< -10 mmHg			
BP = blood pressure				
Note: Orthostatic hypotension requires that conditions (1) and [(2a) or (2b)] are met.				

For subjects who are unable to stand and have the vital signs measured in a sitting or supine position instead of the standing position, the difference between standing and supine values will remain missing.

A listing of subjects with treatment-emergent orthostatic hypotension will be presented.

In addition, a by-subject listing of the physical examination data will be presented.

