4.1. Inclusion Criteria

Each potential subject must satisfy all of the following criteria to be enrolled in the study:

- 1. 1.1. Criterion Modified per Amendments 1 and 5
 - 1.2 Men or WONCBP, aged 18 to 70 years (inclusive). Note: Subjects should be at least 18 years of age or older as per the legal age of consent in the jurisdiction in which the study is taking place.

A WONCBP is defined as:

- Postmenopausal
 - A postmenopausal state is defined as no menses for 12 months without an alternative medical cause. A high follicle stimulating hormone (FSH) level (>40 IU/L or mIU/mL) in the postmenopausal range may be used to confirm a postmenopausal state in women not using hormonal contraception or hormonal replacement therapy.
- O Permanently sterile

 Permanent sterilization methods include hysterectomy, bilateral salpingectomy, bilateral tubal occlusion/ligation procedures, and bilateral oophorectomy.

If reproductive status is questionable, additional evaluation should be considered.

- 2. 2.1 Criterion Modified per Amendments 1, 2, and 5
 - 2.3 Meet DSM-5 diagnostic criteria for MDD, without psychotic features (DSM-5 296.22, 296.23, 296.32, or 296.33), based upon clinical assessment and confirmed by the SCID-CT. In addition, their major depressive episode must be deemed "valid" using the SSQ interview administered by remote, independent raters. The length of the current depressive episode must be ≤18 months.
- 3. 3.1 Criterion Modified per Amendments 1, 3, and 5
 - 3.3 Have had an inadequate response to at least 1 but no more than 3 antidepressants (see the inclusion criterion below), administered at an adequate dose and duration in the current episode of depression, as measured by the MGH-ATRQ. An inadequate response is defined as <50% reduction in depressive symptom severity, as assessed by the MGH-ATRQ. An adequate trial is defined as an antidepressant treatment for at least 4 weeks at or above the minimum therapeutic dose specified in the MGH-ATRQ, for any particular antidepressant. The inadequate response must include the subject's current antidepressant treatment.
- 4. 4.1 Criterion Modified per Amendments 1, 2, 3, and 5

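### Orthostatic hypotension is counted only with a pulse rise above 15 bpm, and no other planned table categorizes the standing-minus-supine blood-pressure change

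*SAP*

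**What the plan says.** SAP 6.3 gives the rule twice. The text reads "Orthostatic hypotension is defined as an absolute decrease in systolic (>20 mm Hg) or diastolic (>10 mm Hg) blood pressure" on standing relative to supine, "with an increase in pulse rate of >15 beats per minute". The note under Table 6 repeats it: "Orthostatic hypotension requires that conditions (1) and [(2a) or (2b)] are met". The pulse condition is thus a deliberate AND, not a slip in one place. The table counts subjects who meet the composite at any time in the double-blind phase and did not have it at baseline. The listing of orthostatic cases follows the same definition.

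Three other outputs can carry blood-pressure information:

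- **Table 5.** "Incidence of treatment-emergent clinically important abnormalities in vital signs during the double-blind phase, as defined in Table 5, will be summarized", with a subject listing. Its blood-pressure limits carry no pulse condition. They compare with baseline rather than with the supine reading, and they also require a low absolute value.
- **Descriptive statistics.** SAP 6.3 says that "supine and standing blood pressure (systolic and diastolic), and BMI will be summarized at each assessment time point by treatment group", with changes from baseline and with minimum and maximum among the statistics.
- **Adverse events.** Protocol 9.6 requires clinically relevant changes to be recorded as adverse events, and SAP 6.1 tabulates all treatment-emergent ones.

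Protocol 9.6 takes pulse and blood pressure in both positions, and the Time and Events Schedule places vital signs at Days 8, 22 and 42 as well as at baseline.

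**The concern.** Safety and tolerability is a primary objective in Protocol 2.1, with vital signs among the named endpoints, and Protocol 1.3 lists dizziness among the most commonly reported adverse events. A reader of a table titled orthostatic hypotension will take it as the count of subjects whose pressure dropped on standing. Under the SAP it is the count of subjects whose pressure dropped and whose pulse also rose by more than 15 bpm. If an arm had many falls with a small pulse response, the table could look clean, and no other planned table would show how often the postural fall itself met the SAP's own blood-pressure thresholds.

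The same rule also governs what counts as new. A change in pulse response alone can turn an unchanged postural fall into a treatment-emergent case.

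**Working it through.** The documents state no event count, rate or power figure for this table, so there is no figure to reproduce. The check is to apply the written rules to readings and see where each falls.

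**Rules (SAP 6.3).** Differences are standing minus supine.

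- Table 6 composite: pulse change > 15 AND (systolic change < −20 OR diastolic change < −10).
- Blood-pressure part alone: systolic change < −20 OR diastolic change < −10.
- Table 5 low limits, applied here to standing values: fall from baseline of at least 20 to a value of 90 or below (read as systolic), or of at least 15 to 50 or below (read as diastolic).

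Two caveats apply to Table 5. Its row labels were not legible in the copy used, so the systolic and diastolic rows are inferred from the limits. The text does not show whether the limits apply to supine values, standing values or both. If they apply to supine values only, Table 5 would not pick up standing falls at all.

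**Readings (assumed for illustration, not trial data).**

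| Case | Supine to standing | Change | Pulse change | Baseline standing | Table 6 | BP part alone | Table 5 |
|---|---|---|---|---|---|---|---|
| A | 140/85 to 105/72 | −35/−13 | +5 | 135/84 | no | yes | no |
| B | 125/80 to 85/65 | −40/−15 | +5 | 122/80 | no | yes | yes |
| C | 125/80 to 100/66 | −25/−14 | +20 | 122/80 | yes | yes | no |
| D | 120/75 to 108/48 | −12/−27 | +8 | 120/76 | no | yes | yes |
| E | 150/90 to 95/60 | −55/−30 | +10 | 148/90 | no | yes | no |

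Case E in full: 95 − 150 = −55, so (2a) is met; 60 − 90 = −30, so (2b) is met; the pulse change of 10 is not above 15, so (1) fails and Table 6 does not count it. For Table 5, 148 − 95 = 53 is at least 20, but 95 is above 90; 90 − 60 = 30 is at least 15, but 60 is above 50. Neither limit is met.

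Of the four falls without the required pulse rise (A, B, D, E), Table 6 flags none and Table 5 flags two (B and D). A and E would surface as individual events only through adverse event reporting.

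**Treatment-emergence.** Take a subject with a 30 mmHg systolic fall and a 10 bpm rise at baseline, then the same 30 mmHg fall and a 16 bpm rise at Day 8. At baseline 10 is not above 15, so orthostatic hypotension is absent. At Day 8, 16 is above 15, so it is present and counted as new. The blood-pressure fall did not change. The pulse condition can therefore add cases as well as remove them.

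**Size.** The share of falls lacking the pulse rise is not given in either document, so no count of affected subjects can be derived.

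**The case against.** The strongest reply is that the composite is explicit, prespecified, the same in text and table, and applied alike in all arms. It contradicts nothing in the protocol, which never defines orthostatic hypotension; Protocol 11.7 promises only the percentage of subjects beyond clinically important limits, and Table 5 supplies that. This stands, and it is why the composite should be kept.

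A second reply concerns specificity. A blood-pressure-only rule flags more chance falls. If one assumes a 5% chance fall per visit, independent over the three post-baseline double-blind visits, 1 − 0.95³ = 1 − 0.857 = 0.143, so about 14% of subjects in every arm would be flagged at least once. That could dilute a contrast between arms. This argues against replacing the composite, but not against showing the two counts side by side.

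A third reply is that relevance is not demonstrated. Protocol 1.1.2 reports no clinically significant, consistent treatment-related effects on vital signs. Dosing is at bedtime, readings are taken on later mornings, and the mean half-life is 2 to 3 hours. Significant or unstable cardiovascular disorders are excluded. All of this is correct and limits the weight of the point.

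Two stronger readings are tempting. A reader might infer that a fall without a pulse rise is flagged in no planned safety table, or survives only in group means. The documents do not support that: Table 5 has no pulse condition and caught two of the four illustrative falls, minimum and maximum are reported, and clinically relevant changes go to the adverse event tables. A reader might also infer that older subjects or those on rate-limiting drugs are the ones missed. Eligibility does run to 70 ("Men or WONCBP, aged 18 to 70 years (inclusive"), and beta-blockers are not on the Protocol Section 8 list, but neither document says who lacks a pulse rise or how many such subjects enrolled.

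**Conclusion.** The narrower point holds. SAP 6.3 leaves a postural fall without a pulse rise above 15 bpm out of the orthostatic table and listing, and no other planned table categorizes the standing-minus-supine change. Such a fall surfaces only if it meets the Table 5 limits or is reported as an adverse event, and reporting depends on symptoms or on the investigator's judgment.

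The rule itself is certain from the text. The comparison with Table 5 rests on inferred row labels and on the assumption that its limits apply to standing values. The number of subjects affected is unknown. Nothing in the efficacy analysis, sample size or type I error is touched, and no data are lost. The documents do not show that the composite is wrong or that it hides a signal in this trial. This is a cheap improvement, not a defect that threatens the trial's conclusions.

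**What to change.** In SAP 6.3 and Table 6, keep the composite and all its thresholds as prespecified. Add one row, and a matching listing, for subjects with treatment-emergent falls meeting (2a) or (2b) regardless of pulse. For that row, judge absence at baseline on the same blood-pressure-only definition, so that a change in pulse response alone cannot create or remove a new case. The two rows together show how much the pulse condition removes in each arm.

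The cost is a sentence in the SAP, one table row and one listing, all from supine and standing readings already collected. The downside is that more chance falls will be flagged, in all arms, so the added row should be read against placebo and not as an absolute rate.
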